#### For partial start dates:

1. If the year is unknown, then do not impute the date but assign a missing value.
2. If the month is unknown, then:
  - a. If the year matches the year of the dose date, then impute the month and day of the dose date.
3. If the day is unknown, then:
  - a. If the month and year match the month and year of the first dose date, then impute the day of the dose date.

#### For partial end dates:

1. If the year is unknown, then do not impute the date but assign a missing value.
2. If the month is unknown, then do not impute the date and mark as ongoing for AE and Concomitant medication.
3. If the day is unknown, then assign the last day of the month.

After implementing the rules above, to determine whether AEs (or medications) with missing start or stop dates are pretreatment or on/after treatment, the following strategy will be used:

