An SAE is any adverse event (appearance of (or worsening of any pre-existing) undesirable sign(s), symptom(s) or medical conditions(s) which meets any one of the following criteria

- is fatal or life-threatening
- results in persistent or significant disability/incapacity
- constitutes a congenital anomaly/birth defect
- requires inpatient hospitalization or prolongation of existing hospitalization, unless hospitalization is for
 - routine treatment or monitoring of the studied indication, not associated with any deterioration in condition
 - elective or pre-planned treatment for a pre-existing condition that is unrelated to the indication under study and has not worsened since signing the informed consent
 - treatment on an emergency outpatient basis for an event not fulfilling any of the definitions of a SAE given above and not resulting in hospital admission
 - social reasons and respite care in the absence of any deterioration in the patient's general condition
- is medically significant, i.e. defined as an event that jeopardizes the patient or may require medical or surgical intervention to prevent one of the outcomes listed above.

All malignant neoplasms will be assessed as serious under “medically significant” if other seriousness criteria are not met.

Unlike routine safety assessments, SAEs are monitored continuously and have special reporting requirements; see Section 7.2.

All adverse events should be treated appropriately. Treatment may include one or more of the following: no action taken (i.e. further observation only); [study treatment/investigational] treatment dosage adjusted/temporarily interrupted; study drug(s) permanently discontinued; concomitant medication given; non-drug therapy given. The action taken to treat the adverse event should be recorded on the Adverse Event CRF.

Once an adverse event is detected, it should be followed until its resolution or until it is judged to be permanent, and assessment should be made at each visit (or more frequently, if necessary) of any changes in severity, the suspected relationship to the study treatment, the interventions required to treat it, and the outcome.

Information about common side effects already known about the investigational drug can be found in the package insert. This information will be included in the patient informed consent and should be discussed with the patient during the study as needed.

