**Version: Final 1.0 Date: 01 Dec 2022**

1. If the start date and stop date are both missing, then the most conservative approach is taken and the AE (or medication) is considered to be treatment-emergent (or concomitant medication).
2. If the start date is missing but the stop date is not missing and is on or after the day of first study dose administration, then the most conservative approach is taken and the AE (or medication) is considered to be treatment-emergent (or concomitant medication).
3. If the start date is missing but the stop date is not missing and is before the day of first study dose and after the date of signed informed consent, then the AE (or medication) is considered to be before treatment (or prior medication).
4. If the start date is not missing but the stop date is missing, then the most conservative approach is taken, and medication is considered to be concomitant while the AE is defined by the start date.

If the adverse event relationship flag is missing, the relationship for the adverse event will be imputed and will be considered as possibly related. If the Adverse Event Severity flag is missing, the severity will be imputed with the maximum severity as “Severe” and if the adverse event is flagged as Serious adverse event and the severity flag is missing then the maximum severity imputed will be “life-threatening”

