### 9.4 Prior and concomitant medication

Prior and concomitant medications will be assessed at screening and at each subsequent study visit. Medications will be coded using WHODDE+ HD DEC 2017 and will be summarized by ATC class (the highest available level), preferred name for the safety population. Patients taking the same medication multiple times will be counted once per medication.

Medication will be classified as prior, If the medication that start and stop prior to the date of received study medication. Medications that are ongoing or ended after the first use of the study medication will be classified as concomitant. If the end date of the medication is unknown, it will also be considered as concomitant. Handling of missing date explained in section (Imputation of missing data [section 8.5.1](#)).

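### Two SAP 8.5.1 rules misclassify when triggered: an SAE with missing severity gets a value outside the protocol's severity scale, and a drug with only a stop year, earlier than the first-dose year, is classed as concomitant

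*SAP*

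**What the plan says.** **Missing severity.** At the end of SAP 8.5.1, an adverse event with no severity flag is set to Severe. For serious events a different value applies: "if the adverse event is flagged as Serious adverse event and the severity flag is missing then the maximum severity imputed will be" life-threatening. Protocol 6.1 defines three severity grades: mild, moderate and severe. The same section uses life-threatening elsewhere, as part of the first SAE criterion: "is fatal or life-threatening". The shells for Tables 14.3.1 and 14.3.3 show Mild, Moderate and Severe and no other severity row.

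**Partial stop dates.** Under the partial end-date rules in SAP 8.5.1, item 2 says: "If the month is unknown, then do not impute the date and mark as ongoing for AE and Concomitant medication". Item 3 says: "If the day is unknown, then assign the last day of the month". The classification steps that follow treat a medication as concomitant in two relevant cases:

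- Step 1, both dates missing: "If the start date and stop date are both missing, then the most conservative approach is taken".
- Step 4, only the stop date missing: "the most conservative approach is taken, and medication is considered to be concomitant while the AE is defined by the start date".

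SAP 9.4 gives the definitions. Prior: "Medication will be classified as prior, If the medication that start and stop prior to the date of received study medication". Concomitant: "Medications that are ongoing or ended after the first use of the study medication will be classified as concomitant". It adds that an unknown end date also leads to concomitant.

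**The concern.** Both rules aim to be cautious, but each can give a result that conflicts with the plan's own definitions.

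For severity, the event treated as most serious receives a value with no place in the severity tables, while a less serious event with the same missing field is counted in the top grade. Read literally, the SAE also falls outside the summary of TEAEs of severe intensity in SAP 9.7.1. The table list has no separate output for that summary, so it is largely the same loss as in Table 14.3.3 and should not be counted twice.

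For medication, a cautious default should settle real uncertainty. If the recorded stop year is before the first-dose year, nothing is uncertain. At stake is the accuracy of the severity rows in the AE summaries, which serve the primary safety objective, and of the split between prior and concomitant drugs.

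**Working it through.** There is no planned figure to reproduce, so the check traces the rules.

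**1. Severity values against the scale and the shells**

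| Event with missing severity | Imputed value (SAP 8.5.1) | Grade in Protocol 6.1? | Row in Tables 14.3.1 and 14.3.3? |
|---|---|---|---|
| Non-serious AE | Severe | Yes | Yes |
| SAE | life-threatening | No | No |

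Take three illustrative patients with five different events. A has a mild AE and an SAE with missing severity. B has a severe AE and an SAE with missing severity. C has one moderate AE. Under the shell footnotes, a patient counts in a row with at least one AE there:

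| | Mild | Moderate | Severe | Events with a severity row |
|---|---|---|---|---|
| As written | 1 | 1 | 1 | 3 of 5 |
| Severe imputed | 1 | 1 | 2 | 5 of 5 |

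The row label in Table 14.3.1 refers to maximum severity. If that means one maximum per patient, and life-threatening ranks above Severe, A and B leave the rows altogether: Mild 0, Moderate 1, Severe 0 as written, against Mild 0, Moderate 1, Severe 2 with Severe imputed. SAP 9.7.1 applies the maximum only to repeats of the same AE. On that text and the footnotes, only the event is lost.

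**2. Year-only stop dates**

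Let Y be the recorded stop year and F the first-dose year. If the month is unknown, the latest possible stop is 31 December of Y. If Y < F, that day is before 1 January of F, and so before first dose. The drug therefore started and stopped before first dose and meets the SAP 9.4 definition of prior, whatever the exact dates.

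Illustration with an assumed first dose of 15 March 2019:

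| Recorded stop | SAP 8.5.1 handling | SAP class | Latest possible stop | Class by SAP 9.4 definition |
|---|---|---|---|---|
| Dec 2018 | Item 3: 31 Dec 2018 | Prior | 31 Dec 2018 | Prior |
| 2018 | Item 2: ongoing | Concomitant | 31 Dec 2018, 74 days before (31 + 28 + 15) | Prior |
| 2015 | Item 2: ongoing | Concomitant | 31 Dec 2015, 1170 days before (366 + 365 + 365 + 74) | Prior |
| 2019 | Item 2: ongoing | Concomitant | 31 Dec 2019 | Cannot be settled |

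The first two rows show the inconsistency: a stop recorded only as 2018 cannot be later than the end of December 2018, yet it is classed differently.

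Ignoring the ongoing mark does not change the result. The stop date stays missing, so step 4 (start known) or step 1 (start also missing) still gives concomitant. Step 3 does not catch the case, because it needs a stop date that is present and falls after consent.

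**3. Size**

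One patient is 1/102 = 0.98% of planned enrolment, or 1/93 = 1.08% of the sample before the dropout allowance. That is an upper bound per row. For medications the shift is zero if the patient already counts in that row, because patients count once per ATC class and preferred term. The documents do not give the number of affected records.

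**The case against.** **Unknown end dates are deliberately treated as concomitant.** The convention appears in 8.5.1 and again in 9.4 and is described as conservative. This stands where the stop falls in the first-dose year. It does not cover a known earlier year. A reader might infer that the whole default is wrong, but the documents do not support that.

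**The tables may be built by form, not by date.** The catalogue has separate listings for prior and current medication (with its own ongoing field) and for concomitant medication, and Tables 14.1.8 and 14.1.9 carry matching titles. If tables follow the form, the drug stays in 14.1.8. SAP 9.4 describes classification by date, so the question is open and the table error is conditional.

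**The shells are only examples.** The catalogue's introduction says so, and a row could be added. But the SAP does not call for one, and it would report a grade that the protocol does not define.

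**The triggers are rare.** Protocol 4.6.8 and 5.3 mainly call for drugs given after enrolment or continuing at start. SAEs are reported within 24 hours, and Protocol 7.1 requires their documentation to be fully verified. This stands, and it keeps the point minor. SAP 9.4 does provide for prior medication at screening, so the drug case can still occur.

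**Stronger readings.** A reader might infer that serious events vanish from the report or that the overall safety counts are wrong. They do not vanish: Listings 16.2.7.1 and 16.2.7.1.1 show each SAE with its seriousness criterion, and severity is not used to count TEAEs, SAEs or the entries in Table 14.3.7. An AE with missing start and a year-only stop would be called treatment-emergent under step 1. A pre-dose year is remote there, because AEs are recorded only after consent and the schedule places consent on Day 1.

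A reader might also infer that the imputed relationship value, possibly related, must be replaced by the no/yes categories of Protocol 6.1. SAP 9.7.1 speaks of the closest relationship, which suggests graded categories on the CRF. The CRF is not among the documents, so only reconciliation can be asked for.

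**Conclusion.** The point holds as a minor correction that matters only when a rule is triggered.

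- **Severity:** the imputed value for an SAE lies outside the protocol scale. Under the shells as drawn it has no row, while a non-serious AE with the same gap counts as Severe.
- **Medication:** a year-only stop before the first-dose year gives concomitant, against the SAP's own definition of prior. The drug reaches the wrong table only if Tables 14.1.8 and 14.1.9 are built from dates.
- **Size:** at most about 1 percentage point per patient per row, possibly zero, with the number of records unknown. Neither rule changes the overall TEAE or SAE counts.

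The conclusion on the medication class rests on no assumed date; 15 March 2019 is illustration only. The severity conclusion assumes that the CRF uses the protocol's three grades, as the shells do.

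**What to change.** In SAP 8.5.1:

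1. Impute Severe, the top protocol grade, for any AE or SAE with missing severity, and delete the separate value for SAEs.
2. For a stop date with unknown month, first compare the stop year with the first-dose year. If it is earlier, class the medication as prior, whether or not the start date is known. Otherwise keep the current rule.
3. Drafting only: the safety paragraph allows imputation of partial dates alone, yet severity and relationship are imputed later in the section. Name both as exceptions, and reconcile possibly related with the relationship categories actually collected.

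The cost is a few lines of SAP text and the matching program logic, with no new data and no new table.

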**Statistical Analysis Plan**  
**Sponsor: Novartis**

**Study Number:** [REDACTED]

**Version: Final 1.0 Date: 01 Dec 2022**

1. If the start date and stop date are both missing, then the most conservative approach is taken and the AE (or medication) is considered to be treatment-emergent (or concomitant medication).
2. If the start date is missing but the stop date is not missing and is on or after the day of first study dose administration, then the most conservative approach is taken and the AE (or medication) is considered to be treatment-emergent (or concomitant medication).
3. If the start date is missing but the stop date is not missing and is before the day of first study dose and after the date of signed informed consent, then the AE (or medication) is considered to be before treatment (or prior medication).
4. If the start date is not missing but the stop date is missing, then the most conservative approach is taken, and medication is considered to be concomitant while the AE is defined by the start date.

If the adverse event relationship flag is missing, the relationship for the adverse event will be imputed and will be considered as possibly related. If the Adverse Event Severity flag is missing, the severity will be imputed with the maximum severity as “Severe” and if the adverse event is flagged as Serious adverse event and the severity flag is missing then the maximum severity imputed will be “life-threatening”

## **8.6 Sample Size Calculation**

Incidence of adverse event data of ACTION study (74.60%) for Rivastigmine patch per day over a 24-week study period in patients with severe AD.

The sample size is determined based on a precession approach considering normal approximation. A sample of 93 subjects will be able to estimate the incidence rate with a maximum error of 10% of the true population proportion with 90% of the cases. We assumed that the true population proportion is 0.746 (what is observed in US44)

Similarly, a sample of 41 subjects will be able to estimate the incidence rate with a maximum error of 10% of the true population proportion with 85% of the cases and sample of 23 subjects of the true population proportion with 80% of the cases.

Considering the drop out of 10% and the true population proportion with 90%, 102 patients shall be enrolled.

## **8.7 Interim Analysis**

No interim analyses are planned.

## **8.8 Statistical Software**

All statistical analyses will be performed with SAS®, Version 9.4 or later.

**Statistical Analysis Plan**  
**Sponsor: Novartis**

Study Number: [REDACTED]

Version: Final 1.0 Date: 01 Dec 2022

## 9 Statistical Analyses

### 9.1 Patient Disposition

Patient disposition will be tabulated with number and percentages of patient's enrolled, dosed, completed the study according to the protocol or discontinued the study prematurely. The patients who prematurely discontinued the study and the reasons for their discontinuation will be presented. The disposition table will be summarized using "screened population".

### 9.2 Demographic Data and Baseline Characteristics

- Age (year)
- Gender
- Height (cm)
- Weight (kg)
- BMI((kg/m^2)
- Baseline MMSE Total Score
- Baseline ADCS-ADL SIV Total score
- Diagnosed with AD

### 9.3 Medical History

All general medical history including complete review of all current and past conditions will be coded using MedDRA version 20.1. General medical history conditions will be summarized by system organ class, preferred term using SAF population. The version of the utilized dictionary will be presented as part of the provided tables and listings. Listing of medical history will be provided.

Patients will be counted only once at the preferred term (PT), only once at the system organ class (SOC), and only once at patient level for the counting of total number of patients with a medical history term. Listings of medical history events for patients in the safety population will be provided.

### 9.4 Prior and concomitant medication

Prior and concomitant medications will be assessed at screening and at each subsequent study visit. Medications will be coded using WHODDE+ HD DEC 2017 and will be summarized by ATC class (the highest available level), preferred name for the safety population. Patients taking the same medication multiple times will be counted once per medication.

Medication will be classified as prior, If the medication that start and stop prior to the date of received study medication. Medications that are ongoing or ended after the first use of the study medication will be classified as concomitant. If the end date of the medication is unknown, it will also be considered as concomitant. Handling of missing date explained in section (Imputation of missing data [section 8.5.1](#)).

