4.6.8 Concomitant treatment

The investigator should instruct the patient to notify the study site about any new medications he/she takes after the patient was enrolled into the study. All medications, procedures and significant non-drug therapies (including physical therapy and blood transfusions) administered after the patient was enrolled into the study must be recorded.

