## 8.3 Definitions

In the following table, the definitions and calculation of derived variables are summarized

Variable / Term	Definition / Way of calculation
Age	Int ((informed consent date – Birth date +1)/365.25)
Baseline	The last valid value prior to the first dose of study treatment
BMI (kg/m2)	Weight (kg) / (Height (m) x Height (m))
Duration of exposure	Treatment end date- treatment start date + 1
Treatment Start Date	Date of dose administration on Day 1 in Investigational Product Log in the CRF
Treatment End Date	The last date from the ‘Investigational Product Log’ form to be considered as treatment end date
Treatment Emergent AE (TEAE)	An AE will be considered as treatment-emergent if the time of onset is on or after the time of the first dose or any AE that exist prior to first dose and if it increased in severity during the study.

	Statistical Analysis Plan Sponsor: Novartis
Study Number: [REDACTED]	Version: Final 1.0 Date: 01 Dec 2022

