**Catalogue of Tables, Listings and Figures**  
**Sponsor: Novartis**

**Study Number: [REDACTED] Version: Final 1.0 Date: 01 Dec 2022**

**Table 14.1.8: Summary of Prior Medications by ATC Class and Preferred Term**

Novartis  
[REDACTED]

*ddmmmyyyy hh:mm*  
*Page x of y*

Table 14.1.8

Summary of Prior and Current Medications by ATC Class and Preferred Term  
(Safety Population)

ATC Class Preferred Term	(N = xx) n (%)
Number of patients with at least one medication recorded	xx (xx.x)
ATC level	xx (xx.x)
Preferred Term 1	xx (xx.x)
Preferred Term 2	xx (xx.x)
.....	.....

N = The total number of patients in the safety population

n = Number of patients with non-missing data within the specific category.

Percentages are based on the total number of patient's under safety population

Patients are counted only once within each ATC class and preferred term

Prior and current medications are coded using WHODDE+ HD DEC 2017

Analysis Dataset: XXXX

Source Listing: Listing xx.x.x

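### SAP 8.5.1 imputes a partial start date without checking a known stop date, so a drug stopped before the first patch can be neither prior nor concomitant under SAP 9.4

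*SAP*

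**What the plan says.** SAP 9.4 defines two classes. For prior: "Medication will be classified as prior, If the medication that start and stop prior to the date of received study medication". For concomitant: "Medications that are ongoing or ended after the first use of the study medication will be classified as concomitant", to which it adds "If the end date of the medication is unknown, it will also be considered as concomitant". It refers to SAP 8.5.1 for missing dates.

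For partial start dates, SAP 8.5.1 rule 2a covers an unknown month: "If the year matches the year of the dose date, then impute the month and day of the dose date". Rule 3a does the same for an unknown day when month and year match those of the first dose. Neither rule mentions the stop date.

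A numbered list then deals with dates still missing after those rules have been applied. Item 3 treats a record with a missing start, and a known stop before first dose and after consent, as pre-treatment or prior. Item 4 covers a known start with a missing stop: the "most conservative approach is taken, and medication is considered to be concomitant while the AE is defined by the start date".

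SAP 8.3 and 9.7.1 call an adverse event treatment-emergent if its onset is on or after the first dose, or if it existed earlier and worsened.

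In the table catalogue, the caption of the Table 14.1.8 shell names prior medications only. The title inside the shell adds current medications, and its footnote reads "Prior and current medications are coded using WHODDE+ HD DEC 2017". Listing 16.2.4.3 shows the same split between heading and inner title.

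**The concern.** Setting a partial start to the first-dose date is a cautious choice when nothing else is known. When the record has a stop date before the first dose, it contradicts known data: the drug is given a start after it ended. The 9.4 definitions do not catch such a record. The start test removes it from the prior class and the stop test keeps it out of the concomitant class.

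The drugs exposed are those begun and ended earlier in the year of the first patch, which could include an earlier Alzheimer treatment. Table 14.1.8 is meant to describe that background in a single-arm study, so losing those records makes the description incomplete. Two programmers could also repair the gap in different ways and produce different tables from the same data.

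**Working it through.** No sample size or error rate is involved, and the plan has no figure to reproduce. The check applies the rules as written to test records.

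**Inputs.** Prior and concomitant definitions: SAP 9.4. Partial-date rules and the four-item list: SAP 8.5.1. Assumed dates, for illustration only: first patch 15 Sep 2019, last patch 20 Dec 2019.

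**Tests.** Prior: start < 15 Sep 2019 and stop < 15 Sep 2019. Concomitant: ongoing, or stop unknown, or stop > 15 Sep 2019.

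| Record | Start after 8.5.1 | Stop | Prior? | Concomitant? |
|---|---|---|---|---|
| A. Start in unknown month of 2019 | 15 Sep 2019 (rule 2a) | 10 Mar 2019 | No, start not before first dose | No, ended before it |
| B. Start on unknown day of Sep 2019 | 15 Sep 2019 (rule 3a) | 5 Sep 2019 | No | No |
| C. Start 1 Jan 2019 | unchanged | 15 Sep 2019 | No, stop not before first dose | No, stop not after it |
| D. Start 1 Jan 2019 | unchanged | ongoing | No | Yes |
| E. Start 2 Jan 2020 | unchanged | 9 Jan 2020 | No | Yes |

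In A the imputed start falls 189 days after the stop (21 days left in March + 30 + 31 + 30 + 31 + 31 + 15). In B it falls 10 days after. Both records end up in neither class. C is also unclassified, although no date was imputed, because 9.4 leaves the day of first dose between its two definitions.

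**Does item 3 of the 8.5.1 list rescue A or B?** No. It applies only if the start is still missing after the partial-date rules, and in A and B it has just been filled. For A the stop would also have to fall after consent. Had B's start been wholly missing, with consent before 5 Sep, item 3 would have made it prior. The record with more information is handled worse.

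**Adverse events.** SAP 8.5.1 applies the same date rules to adverse events. Take an event with onset on an unknown day of Sep 2019 that ended on 5 Sep. Its onset becomes 15 Sep, which is on the first-dose date, so it is treatment-emergent by definition although it was over before treatment. This needs a gap between consent and first patch: Protocol 6.1 counts events only after consent, and the visit schedule puts consent on Day 1.

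**After the change proposed under fix.** A: start 1 Jan 2019, stop 10 Mar, prior. B: start 1 Sep 2019, stop 5 Sep, prior. C: ended on the first-dose date, concomitant. D and E are unchanged. The adverse event gets onset 1 Sep and is no longer flagged.

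**The case against.** Item 3 shows that the authors meant the stop date to govern, and a careful programmer would probably follow that intent. The fault needs three things together: a partial start, in the year or month of first dose, with a known earlier stop. All data also go into the listings (SAP 8.1), so the record is not lost from the report. No hypothesis is tested, and the efficacy, compliance, skin and UTI summaries do not use this classification. All of this stands and keeps the point small. It does not make the rules correct as written.

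Two stronger readings are tempting, and the documents do not support them.

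- A reader might infer that a drug begun after the last patch (record E) is misclassified, so that a switch appears as combination use. But 9.4 defines concomitant without an upper limit, and the treatment-emergent definition is equally open-ended. This is a convention. Nor are Tables 14.1.8 and 14.1.9 the only counts that bear on added Alzheimer therapy. Protocol 4.6.10 makes adding a second such treatment a reason for early termination, and Table 14.1.1 counts withdrawal reasons, provided the CRF reasons follow the protocol. Listing 16.2.8.4 records added or changed Alzheimer medication by visit. The 10% drop-out allowance (0.10 × 102 = 10.2 patients) does not measure the size of this: it does not say how many stop the patch, start another drug and have it recorded.
- A reader might infer from the word current in Table 14.1.8 that drugs ongoing at Day 1 will be missed or counted twice. SAP 9.4 is clear that ongoing drugs are concomitant, and the table's own caption says prior only. This is a title inconsistency.

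**Conclusion.** The gap is real and narrow. As written, SAP 8.5.1 and 9.4 leave two kinds of record unclassified: a drug with a known stop before first dose whose partial start is imputed to the first-dose date, and a drug stopped on the first-dose date. Both drop out of Tables 14.1.8 and 14.1.9. The same imputation could wrongly flag an adverse event as treatment-emergent, which touches the primary safety summary but should be rare.

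The number of records cannot be derived, because the documents do not say how often dates will be partial. The conclusion assumes that drugs already stopped are recorded. SAP 9.4, Protocol 8.2 and the stop-date column of Listing 16.2.4.3 imply this, although Protocol 5.3 mentions only drugs continuing at the start. The point is a worthwhile tidy-up of mainly descriptive tables and threatens no main result.

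**What to change.** - **SAP 8.5.1, partial start dates.** Apply the end-date rules first. Impute the first-dose date only if the stop date is missing or on/after first dose. Otherwise use the earliest date that the partial date allows, never later than the stop date. Apply this to medications and adverse events alike.
- **SAP 9.4.** Define prior as stopped before first dose, and concomitant as ongoing or ended on or after first dose. Keep the existing rule for unknown end dates.
- **Catalogue, minor.** Retitle Table 14.1.8 and Listing 16.2.4.3 as Prior Medications throughout, to match 9.4.
- **Optional.** A separate class for drugs started after the last patch could be added if the sponsor wants it. Its absence is not an error.

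The cost is a few lines of SAP text and a date comparison in the program. No new data are needed.
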